## **11. Description of the Study Areas/Regions, Design, Materials and Methods:**

***Study Sites.*** Sites engaged in research include the University of Washington, the University of Michigan, Nyanza Reproductive Health Society (NRHS), and the Nyanza, Rift Valley, and Western Kenya LGBTI Network (NYARWEK). Participant recruitment will occur through the NYARWEK Network. Enrollment, all study visits, and clinical care, including PrEP services provided according to the most recent Kenyan Ministry of Health guidelines, will take place in private rooms at the ***Anza Mapema*** Clinic. Intervention delivery will take place at NYARWEK, at private sites used by NYARWEK organizations, or at a meeting space agreed upon and deemed private and safe by both the participant and a ***Shauriana*** peer facilitator trained to deliver the intervention. In-person research team meetings to monitor the study will also be held in private rooms at the ***Anza Mapema*** Clinic, NYARWEK, or at private sites used by NYARWEK organizations. A description of each site's facilities and other resources are included in “Appendix B: Facilities & Other Resources.”

***Study Population.*** The proposed Aim 1 pilot will include 10 adult HIV-negative GBMSM. The proposed Aim 2 intervention trial will include a population of 60 adult HIV-negative GBMSM, all of whom will be recruited in Kisumu, Kenya. The study team and peer facilitators trained to deliver the intervention will also participate in data collection, by providing feedback on intervention feasibility at routine study team meetings that will be minuted.

***Study Design.*** The Aim 1 work will be a prospective pilot of the intervention and of study procedures other than laboratory testing, in a small group of 10 men over a 3-month period, with visits at baseline, month 1, and month 3. During this pilot test, intervention and clinic visit procedures, including data collection tools, will be revised and improved as needed according to feedback on feasibility, comprehension, burden on participants, and acceptability among pilot participants. The Aim 2 work will be an RCT of the final ***Shauriana*** intervention, to test its acceptability, feasibility, and safety and estimate its initial effect size compared to standard care. The final phase of this study will consist of data analysis and dissemination activities.

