***Recruitment.*** Subjects for the Aim 1 Pilot and the Aim 2 intervention trial will be recruited using existing NYARWEK peer networks, snowballing and venue-based referrals. All interested and potentially eligible subjects identified by the NYARWEK team will be given a business card of

the NYARWEK peer facilitator they were in contact with and referred to the *Anza Mapema* clinic for eligibility screening.

Enrolment targets are presented in Table 1. If a participant tests positive for HIV infection at baseline or at any follow-up visit, he will be withdrawn from this study and undergo counselling and referral to the HIV clinic of his choice. Participants who withdraw before or test positive at the month 1 visit will be replaced; replacement participants in the RCT will undergo randomization and not necessarily be assigned to the arm to which the participant they replace was assigned.

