**Table 1. Overview of Participant Enrolment**

Stage	Pilot Test (Aim 1)	Feasibility RCT (Aim 2)
Purpose	Standardization of intervention	Initial testing of feasibility, tolerability, acceptability, and safety; estimate of effect size
Group	10 HIV-negative GBMSM participants	60 HIV-negative GBMSM participants

**Eligibility Screening.** A brief permission script will be used to confirm consent for screening. Basic sociodemographic data (age, sex), a brief risk behavior assessment, and reasons for screening out or failing to enroll will be noted. Men who are found to be ineligible will be referred by *Anza Mapema* staff to HIV prevention or care programming as indicated, including risk reduction counseling, condoms and lubricants, STI screening and treatment, programmatic PrEP if eligible and interested, and HIV care for men who self-report as HIV-positive. Men who are eligible will undergo an informed consent process as described in section 12 (Ethical Considerations).

**Inclusion criteria:** Men recruited for each study aim must meet all of the following criteria:

- Biologically male at birth and identifies as male, according to self-report
- 18 to 35 years of age
- Resident in the Kisumu area for  $\geq 12$  months
- Reports anal intercourse with a man in the past 3 months
- Not currently taking PrEP for HIV prevention in the past 3 months
- Willing to provide complete locator information
- Willing to undergo all study procedures, including HIV testing and counselling
- Not currently participating in any HIV prevention or vaccine study
- Planning to remain in the study area for at least 6 months

*For the pilot study only, men will be required to speak English, in order to expedite the study team's analysis of feedback from these participants in preparation for the RCT. Of note, approximately 50%-60% of young MSM in Kisumu speak English.*

**Exclusion criteria:** Men who meet any of the following criteria will be excluded from this study:

- Unable to understand the study purpose and procedures
- Unwilling to adhere to study procedures

- Currently under the influence of alcohol or drugs
- Prior diagnosis of HIV infection

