Men who screen out or decline enrolment will be reimbursed KSh 350 for transportation to the clinic. Locator information will be collected from all enrolled participants to ensure they can be traced in the event of a missed visit or lab result needing action. In addition, the Anza Mapema clinic provides the option for participants to use iris scanning rather than a study card with their ID number as a means of identification when they present to the clinic. This biometric identification method has been found to be more acceptable to the target population than fingerprint scanning, and helps avoid duplicate enrolments across studies. For study forms that include the recruitment script and eligibility screener and checklist please see "[Appendix C: Eligibility Screener and Checklist.](#)"

***Aim 1 Procedures: Piloting and Standardization of the Shauriana Intervention.*** The overall objective of this phase is to pilot test and standardize our empirically-based, targeted sexual health intervention for Kenyan GBMSM at risk for acquiring HIV. Objectives of the pilot test phase will be to a) assess acceptability of intervention components to the target population; b) test the adequacy of intervention materials and research instruments; and c) monitor fidelity of provider implementation. We will recruit 10 HIV-negative, PrEP-naïve GBMSM who are willing to undergo all intervention procedures at a scheduled roll-out date and provide detailed feedback after each intervention session. Recruitment will be achieved through outreach by the NYARWEK team, with screening and enrolment at the *Anza Mapema* clinic as described above.

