## **12. Ethical Considerations:**

***Human Subjects Involvement and Characteristics:*** The proposed research is non-exempt human subjects research. Prisoners and children under 18 years of age will not be included. Precautions will be taken as below regarding potential subjects with low literacy. All procedures will be conducted in accordance with 45 CFR Part 46. Protocols will be approved by

the Human Subjects Research Committees (HSRC) at the University of Washington (UW) and by the Maseno University Ethics and Research Committee (MUERC) in Kisumu, Kenya. During both research stages (pilot test and RCT), we will actively solicit feedback from GBMSM participants, as well as from the study team (clinic staff and peer facilitators) regarding the feasibility of the intervention components. In addition, we will hold ongoing discussions with the Anza Mapema Community Advisory Board, within the NYARWEK member network, and with our ethical review boards to ensure the relevance and ethical conduct of the research.

The proposed Aim 1 study will include a population of 10 adult HIV-negative GBMSM recruited in Kisumu, Kenya. The proposed Aim 2 study will include a population of 60 adult HIV-negative GBMSM recruited in Kisumu, Kenya. To be eligible for the *Shauriana* intervention pilot or trial, men must be biologically male at birth and male-identifying, 18 to 35 years of age, resident in the Kisumu area for  $\geq 12$  months, report anal intercourse with a man in the past 3 months, and be willing to provide complete locator information and undergo all study procedures, including HIV testing and counseling (HTC). In addition, men should not be currently participating in any HIV prevention or vaccine study and be planning to remain in the study area for at least 6 months. Men will be excluded if they are unable to understand the study purpose and procedures or unwilling to adhere to study procedures or currently under the influence of alcohol or drugs (assessed by clinic staff during screening) or have a prior diagnosis of HIV infection.

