## **16. Timeline/Time Frame:**

Aims 1 and 2 of the project (pilot phase and trial of the *Shauriana* intervention) will occur over an 18-month period, from the time all ethical approvals are in place. Piloting will take place in months 1-5 of the proposed work, after training of the peer facilitators and of the *Anza Mapema* Clinic staff on the research protocol. Recruitment for the RCT would take place over months 6-12, with 6-month follow-up for each enrolled participant. As work progresses, we will present abstracts at international and national conferences and submit manuscripts to top-tier journals with an audience inside and outside of Africa.

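### The RCT entry rules bar only current study participation, so a man who completed the Shauriana pilot can be randomised, including to standard care

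*Combined protocol and SAP*

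**What the plan says.** Section 11 (Eligibility Screening) gives a single list for both phases: "Men recruited for each study aim must meet all of the following criteria". The only RCT-versus-pilot difference stated there is that pilot men must speak English. The rule on other studies is "Not currently participating in any HIV prevention or vaccine study", and Section 12 repeats it: "men should not be currently participating in any HIV prevention or vaccine study". The PrEP rule in Section 11 is "Not currently taking PrEP for HIV prevention in the past 3 months"; the eligibility summary in Section 12 does not mention it. Neither section lists past receipt of Shauriana.

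Section 11 (Study Design) describes the pilot as run "in a small group of 10 men over a 3-month period", and Section 12 says all pilot men receive the intervention. Section 16 states "Piloting will take place in months 1-5 of the proposed work" and places RCT recruitment in months 6-12. On recruitment, Section 11 says: "Subjects for the Aim 1 Pilot and the Aim 2 intervention trial will be recruited using existing NYARWEK peer networks, snowballing and venue-based referrals".

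Three identity checks are described:
- iris scanning, which is optional and "helps avoid duplicate enrolments across studies" (Section 11);
- a registration form intended to prevent duplicate enrolment (Section 12);
- a master file linking names to numbers, checked daily for duplicates (Section 12).

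**The concern.** The word *currently* does all the work in the rule, and the timeline makes it inactive for pilot men by the time the RCT opens. A former pilot man assigned to standard care would be a control who has already had the four weekly peer sessions. One assigned to Shauriana would be receiving it a second time.

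The PrEP rule also filters who can return. It removes pilot men who took up PrEP and stayed on it, and leaves those who never started or who stopped more than 3 months before.

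Two things that Aim 2 is meant to deliver are exposed. The first is the initial effect size on PrEP uptake and drug levels, which Section 13 intends for the design of a larger study. The second is acceptability, a primary outcome compared between arms at months 3 and 6, where a repeat participant's rating is not a first impression.

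**Working it through.** **Inputs.** Pilot size 10, RCT size 60 with 30 per arm, 1:1 allocation in blocks of 4 (all Section 11). The plan states no power, alpha or effect size, so there is no sample-size calculation to reproduce. Its allocation figure checks: 60 / 4 = 15 blocks, and 15 × 2 = 30 per arm.

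**Step 1: is a former pilot man eligible as written?** Follow-up of 3 months inside months 1-5 is over before month 6, so the rule on current participation no longer applies to him. The criteria on age, residence, recent anal intercourse, PrEP use, locator information and plans to stay all apply again, and he may or may not meet them. No exclusion criterion refers to earlier pilot participation. If he meets the rest, he is eligible.

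**Step 2: how many controls could be affected?** Let m be the number of pilot men who re-enter. The number landing in the control arm is treated as hypergeometric (60 men, m of them former pilot men, 30 controls), with mean m/2.

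| m | Expected in control | Share of 30 controls |
|---|---|---|
| 10 | 5 | 16.7% |
| 5 | 2.5 | 8.3% |
| 2 | 1 | 3.3% |

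With m = 10 the 95% range is 2 to 8 controls, so 5 is an expectation and a single allocation could differ. With m = 2 the chance of at least one pre-treated control is about 75%.

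**Step 3: how far does the arm difference shrink?** Let d be the true difference among men new to the intervention. On average a fraction m/60 of each arm are former pilot men.

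- *Full carry-over:* former pilot men look treated in both arms. The control mean rises by (m/60)d, and the difference becomes d(1 − m/60).
- *Non-response:* former pilot men look untreated in both arms. The intervention mean falls by (m/60)d, and the difference is again d(1 − m/60).

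Either way the expected shrinkage is m/60: 10/60 = 16.7%, 5/60 = 8.3%, 2/60 = 3.3%. Partial carry-over in controls, with full response in the intervention arm, gives less.

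**Step 4: illustration.** Take 10.2% as the control rate, which is the share of visits with protective drug levels in the earlier Anza Mapema PrEP cohort (Section 8). Assume 30% under Shauriana; this figure is not in the plan. Then d = 30 − 10.2 = 19.8 percentage points.

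- m = 10: 19.8 × (1 − 10/60) = 16.5
- m = 5: 19.8 × (1 − 5/60) = 18.15
- m = 2: 19.8 × (1 − 2/60) = 19.1
- m = 10 with half carry-over in controls: 19.8 × (1 − 5/60) = 18.15

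**The case against.** The strongest reply is that the plan already guards against this. Section 12 says the registration form is used to prevent duplicate enrolment, not merely to detect it, and one master file is checked daily. Pilot and RCT are components of one protocol, so staff could well treat a returning pilot man as a duplicate. The clinic that would screen him also ran his pilot visits. Appendix C, the operative screener, is not reproduced and may ask the question. This lowers the likelihood of re-entry and the confidence in the point. It does not close the gap, because no text says that pilot-then-RCT entry counts as a duplicate or makes a man ineligible.

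A second reply is that the consequence is small. Uptake and drug levels are secondary outcomes, and Section 11 says the trial is not powered for effect. Section 15 cites more than 600 HIV-negative men recruited earlier, so the return of most of the ten is improbable. This stands as to size. Section 15's contamination paragraph, however, deals with overlapping networks. Holding sessions away from the clinic does nothing for a control who has already had them, and the exit manipulation checks come after randomisation.

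Three stronger readings are tempting and are not supported:

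- *All ten pilot men can be randomised as a group.* The other criteria apply again, and the PrEP rule removes some of the men.
- *Non-responders in the intervention arm add to the carry-over loss.* Randomisation puts the same kind of man in both arms. Exceeding m/60 on average would need carry-over in controls and non-response in intervention men at the same time.
- *The damage cannot be repaired in analysis.* Pilot participation is fixed before randomisation, so dropping these men from both arms keeps the comparison a randomised one.

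**Conclusion.** The gap holds as one of eligibility wording. Applied as written, the criteria admit a former pilot man who meets the other conditions, and nothing keeps him out of the standard care arm. Re-entry is capped at 10 of 60 men. The expected loss in the between-arm difference is at most about 17%, falling to 8% if five return and 3% if two return.

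These shares assume even allocation on average and either full carry-over or complete non-response. Carry-over is possible, not established, and the documents give no basis for the number who would return. The acceptability comparison is affected in kind, by an amount that cannot be calculated from the plan. Confidence is medium because Appendix C is not visible. The change is worth making because it is nearly free.

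**What to change.** Add to the RCT exclusion criteria in Section 11, and to the summary in Section 12: *Previously took part in the Aim 1 Shauriana pilot.* Make it a screening step by checking each candidate against the existing registration form and master ID file before consent and randomisation. Align Appendix C with this if it does not already ask. Section 12 destroys identifiers only after the study is completed, so the look-up should be possible throughout RCT enrolment.

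If a pilot man is randomised despite this, record it and report a sensitivity analysis that omits such men from both arms.

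The cost is one eligibility line, one look-up per candidate, and at most 10 men lost from the recruitment pool. The RCT stays at 60 (30 + 30), with no pre-treated controls from this source. The sensitivity analysis, if needed, would lose at most 10 men (60 − 10 = 50).
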